5.1 Overview

Patients will be randomized in a 1:1 fashion to one of two treatment arms:

- Augmentation of current daily dose of oral loop diuretic + 30 mg of oral Tolvaptan daily
- Augmentation of current daily dose of oral loop diuretic + placebo of oral Tolvaptan daily

The study oral treatment regimen will begin on the day of randomization and continue for a total of 8 days. Patients will have study medication initiated in a hospital setting and will undergo monitoring during their baseline visit according to the presence or absence of hyponatremia and change in serum sodium from baseline during their baseline visit.

Patients will return two days after randomization for their first follow-up visit on Day 3. At this time they will undergo follow-up evaluation of their heart failure state including determination of body weight, vital signs and assessment of clinical evidence of congestion. Patients will return again on Day 8 for their second and final follow-up visit. Following study assessments at that the visit, the randomized treatment period will end and the patient will

be continued on appropriate diuretic therapy alone with the specific type and dosing of these agents being determined by the treating physician.

All patients will have a Day 30 follow up phone call to establish vital status, determine occurrence of hospitalizations and ED visits, assess adverse events, review heart failure symptoms, and review changes in cardiovascular medications since Visit 3.

5.2 Randomization

All patients will be randomized using a block design to ensure roughly equal distributions of patients into each arm of the trial. Randomization will be stratified by clinical site.

5.3 Blinding

This study will be double blinded. Tolvaptan or matching placebo will be supplied by Otsuka America Pharmaceutical, Inc. The pharmacist at each institution will be unblinded to assure dispensation of the correct treatment following the stratified (by site) block design.

5.4 Treatment Arms

Patients will be randomized in a 1:1 fashion to one of two types of treatment:

- Augmentation of current dose of loop diuretic + 30 mg of oral tolvaptan daily
 - Or
 - Augmentation of current dose of loop diuretic + placebo for tolvaptan

Doses of loop diuretics will be standardized to mg equivalents of furosemide based on 40 mg of furosemide for each 1 mg of bumex and 2 mg of furosemide for each 1 mg of torsemide. Augmentation of current dose of loop diuretic will be defined as doubling the current dose of oral loop diuretic if the total daily dose of loop diuretic is \leq 120 mg furosemide equivalents. If the total current oral dose of loop diuretic is $>$ 120 mg then the augmented dose of will be 50% of the current oral dose of loop diuretic + the current oral dose of loop diuretic in furosemide mg equivalents.

5.5 Patient Safety

5.5.1 General Considerations.

Investigators should follow the randomized treatment strategy for the 8 days of treatment. However, as always, the patient's safety, as assessed by clinical evaluation of the study investigators, will take priority over treatment assignment and management based on adherence to the study protocol. Patients who are experiencing inadequate treatment response in terms of relief of congestion may have unscheduled visits as required. They may be treated with more aggressive measures including additional diuretic and may be hospitalized according to investigator judgment. Patients will also be evaluated for excessive decongestion and volume

depletion during the study and may have changes in study medication and augmented loop diuretic as a result. Patients with this possibility may also have additional laboratory assessment and follow-up visits as needed. Patients may continue to be seen for face to face visits after their Day 8 study visit based on investigator judgment of volume status and clinical course.

The study drug (Tolvaptan or placebo) will be stopped prior to the 8 days of planned therapy as per the study protocol or if the study investigator believes in their judgment that the rate of rise of serum sodium is inappropriately rapid or if serum sodium increases to >145 mEq/L in the setting of volume depletion.

5.5.2 Patient Monitoring after Initial Administration of Study Drug

All patients will be observed for at least 8 hours in a hospital setting following the initial administration of randomized therapy. As part of this monitoring they will be observed for adverse neurological events including dysarthria, dysphagia, behavioral disturbance, and muscle weakness.

5.5.3 Monitoring Serum Sodium after Initial Dosing of Study Drug

To aid in monitoring the safety and clinical response following the first dose of study drug, patients will be divided into those with and without hyponatremia based on results from blood samples collected at baseline before receipt of study drug. Serum sodium levels at screening will be evaluated to help identify patients likely to have this degree of reduction in serum sodium at baseline. Hyponatremia will be defined as a serum sodium < 135 mEq/L as measured at the baseline/randomization visit (Visit 1). Hyponatremic patients will be more closely monitored during the baseline visit for possible overcorrection of serum sodium as described below

Patients with No Hyponatremia.

At Visit 1, patients without hyponatremia will be observed for the occurrence of any adverse events for 8 hours in a hospital setting after initial administration of study drug (Figure 2). Patients free of adverse events and clinically stable from a volume standpoint will leave the facility and return for follow-up as outlined below.

Baseline Visit Safety Assessment

[figure not shown]
[figure not shown]

Figure 2

Patients with Hyponatremia. At Visit 1, patients with hyponatremia will have a repeat determination of serum sodium performed from a blood sample taken 6 hours post initial study drug administration (Figure 3). Patients with an increase in serum sodium > 6 mEq/L at 6 hours will require additional monitoring of serum sodium for 24 hours, they will also receive D5W as outlined in detail in Section 6.2. Patients with an increase in serum sodium > 6 mEq/L will not receive additional doses of study medication but will otherwise complete the study as planned.

Baseline Visit Safety Assessment

5.6 Additional Monitoring of Serum Sodium During the Study.

All study patients will have follow-up at 48 hours (Visit 2) with clinical assessment of volume status including evaluation for volume depletion. All patients will have follow-up determination of serum sodium, other electrolytes and renal function at this visit to complement their clinical evaluation and to address the possibility of overcorrection of serum sodium.

All patients will return for a final follow-up visit at 8 days (Visit 3). At this visit all patients will have clinical assessment of volume status including evaluation for volume depletion. All patients will also have determination of serum sodium, other electrolytes and renal function at this visit to complement their clinical evaluation.

6. Study Methodology - See Appendix A

6.1 Screening and Enrollment

6.1.1 Study Screening

Outpatients seen at the participating centers with signs and symptoms consistent with worsening chronic heart failure will be screened by site study personnel for possible entry into the trial. Patients found to meet eligibility criteria will be approached regarding the study and consented for enrollment if they agree to participate. Patients are expected to be enrolled and randomized within 24 hours of informed consent.

6.1.2 Study Enrollment and Estimated Enrollment Period

The sample size for the study is 40 patients. The projected timeline for enrollment is approximately 12 months.

6.2 Baseline Procedures

6.2.1 Randomization

All study subjects will be randomized in a 1:1 fashion to one of the two treatment groups.

6.2.2 Baseline Assessments

At the time of randomization, all study subjects will undergo:

- History and physical examination focused on signs and symptoms of congestion
- Assessment of the degree of congestion and dyspnea present
- Vital signs (including blood pressure and body weight)
- Documentation of current cardiovascular medications
- Measurement of Creatinine, BUN, electrolytes, and serum osmolarity
- Serum pregnancy test for women of child bearing potential

6.2.3 Baseline Blood Sampling

- Blood samples will be obtained prior to the patient receiving study drug/placebo
- A blood sample (20 mL) will be collected for assay of routine clinical labs and copeptin determination
- An optional blood sample (30 mL) will be collected for potential future biomarker and Omic analysis (including DNA and RNA)
- A urine sample (5 mL) will be collected for later measurement of biomarkers, electrolytes and osmolarity and other analytes

6.2.4 Follow-up Observation at Baseline Visit

All patients will initiate study drug tolvaptan/placebo in a hospital setting.

6.2.5 Observation at Baseline Visit - Patients without Hyponatremia

- Patients who are not hyponatremic at baseline will be monitored for 8 hours for adverse effects and changes in vital signs suggestive of potential volume

depletion (orthostatic decline in blood pressure and increases in heart rate) and intake and output. Review of these findings will aid in identification of patients who may be more likely to have overcorrection of serum sodium due to excess aquaresis and inadequate per oral intake. Any patient without hyponatremia at baseline who is clinically suspected to have overcorrection of serum sodium will have repeat determination of serum electrolytes and renal function at 6 hours post initial dose of tolvaptan/placebo. Results of these labs will be reviewed prior to their discharge from the hospital setting. Any patient subsequently found to have an increase in serum sodium > 6 mEq/L will be managed as indicated below for patients with baseline hyponatremia and a similar increase in serum sodium.

6.2.6 Observation at Baseline Visit - Patients with Hyponatremia

- Patients who are hyponatremic at baseline will have repeat determination of serum sodium 6 hours after their initial dose of study drug. Any patient found to have a rise in serum sodium of > 6 mEq/L at the 6 hour time point will receive treatment with intravenous D5W. Intravenous D5W will administered at the rate of 3 mL/kg per hour (210 mL for a 70 kilogram patient) which is expected to reduce serum sodium from 1 to 2 mEq/L per hour.
- Patients with this degree of early increase in serum sodium will have repeat serum sodium and other electrolytes plus BUN and Creatinine determined at 2 hour intervals during D5W administration. Administration of D5W will stop when the patient is at least 14 hours post their initial dose of study drug and the serum sodium is < 8 mEq/L above their baseline value.
- Patients with this degree of early increase in serum sodium will be observed for a minimum of 24 hours after their initial dose of study medication. They will also have repeat determination of serum sodium and other electrolytes plus BUN and Creatinine 20 hours after their initial dose of study medication and these values will be reviewed prior to their discharge from the hospital setting. If their serum sodium remains < 12 mEq/L above baseline at the 20 hour blood draw and they are clinically stable, they will be discharged from the hospital setting at the 24 hour point. In the rare event that the patient is found to have a 20 hour serum sodium that is ≥ 12 mEq/L from their baseline, they will receive additional D5W as above with repeat determinations of serum sodium until their value is $<$

12 mEq/L above their baseline. At that time if they are clinically stable then they will be discharged from the hospital setting.

- Patients found to be hyponatremic will also be monitored for development of symptoms during the study related to reduced serum sodium. As a precaution, patients with symptomatic hyponatremia are excluded from the study. Patients with heart failure who present with hyponatremia are very commonly asymptomatic and the condition is chronic and does require therapy to reverse the hyponatremia per se. Patients with heart failure and chronic hyponatremia rarely become symptomatic. Patients enrolled in the study with asymptomatic hyponatremia will be cautioned to monitor for changes in mental status, nausea, and lethargy between their baseline visit and follow-up visits. Patients will be instructed to contact the study investigators should these symptoms develop and they will be seen for follow-up evaluation as needed.

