4. All patients will initiate study drug tolvaptan/placebo in a hospital setting.
5. Patients who are not hyponatremic at baseline will be monitored for 8 hours for adverse effects and changes in vital signs suggestive of potential volume depletion (orthostatic decline in blood pressure and increases in heart rate) and intake and output. Review of these findings will aid in identification of patients who may be more likely to have overcorrection of serum sodium due to excess aquaresis and inadequate per oral intake. Any patient without hyponatremia at baseline who is clinically suspected to have overcorrection of serum sodium will have repeat determination of serum electrolytes and renal function at 6 hours post initial dose of

tolvaptan/placebo and these labs will be reviewed prior to their discharge from the hospital setting. Any patient subsequently found to have an increase in serum sodium > 6 mEq/L will be managed as indicated in points 6 to 9 that follow.

6. Patients who are hyponatremic at baseline will all have repeat determination of serum sodium 6 hours after their initial dose of study drug. Any of these hyponatremic patients found to have a rise in serum sodium of > 6 mEq/L at the 6 hour time point will receive treatment with intravenous D5W designed to limit further increases in serum sodium. Intravenous D5W will administered at the rate of 3 mL/kg per hour (210 mL for a 70 kilogram patient) which is expected to reduce serum sodium from 1 to 2 mEq/L per hour.
7. Patients with this degree of early increase in serum sodium will have repeat serum sodium and other electrolytes plus BUN and Creatinine determined at 2 hour intervals of D5W administration. Administration of D5W will stop when the patient is at least 14 hours post their initial dose of study drug and the serum sodium is < 8 mEq/L above their baseline values.

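### The D5W rescue rule for early sodium overcorrection has no lower sodium limit; whether a patient would fall below baseline depends on whether the stated hourly fall is net, which the protocol does not say

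*Combined protocol and SAP*

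**What the plan says.** Section 6.2.6 (first two bullets) and section 10.1 items 6-7 give the same rule.

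- **Start:** a rise of more than 6 mEq/L at hour 6.
- **Rate:** 3 mL/kg per hour, "which is expected to reduce serum sodium from 1 to 2 mEq/L per hour".
- **Monitoring:** sodium every 2 hours during the infusion.
- **Stop:** two conditions together. "Administration of D5W will stop when the patient is at least 14 hours post their initial dose of study drug", and, as item 7 puts it, "the serum sodium is < 8 mEq/L above their baseline values".
- **Purpose:** item 6 adds that these patients "will receive treatment with intravenous D5W designed to limit further increases in serum sodium".

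Section 6.2.5 extends the rule to patients without baseline hyponatremia: "Any patient subsequently found to have an increase in serum sodium > 6 mEq/L will be managed as indicated below".

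Later thresholds are also upper limits. At hour 20, 6.2.6 allows discharge at hour 24 if sodium is less than 12 mEq/L above baseline and the patient is clinically stable. At Day 3, a rise above 18 mEq/L prompts hydration or more D5W at the investigator's discretion.

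Three of these thresholds are worded inconsistently:

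- 6.2.6 gives more D5W at hour 20 for a rise of 12 or more; 10.1 item 8 says more than 12.
- 6.2.7 states the 18 mEq/L threshold without reference to baseline; 10.1 item 9 includes it.
- The Appendix A footnote states the 12 mEq/L threshold without reference to baseline.

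**The concern.** A patient whose rise is above 6 but below 8 meets the sodium half of the stopping rule when the infusion starts. As long as the rise stays below 8, only the clock ends D5W. The 2-hourly values are collected, but no low value or rate of fall is tied to an action. A value below baseline would also pass the sodium part of the 20-hour check.

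Overcorrection is the risk section 10.1 treats as unique to tolvaptan, and this is its rescue rule. The protocol writes down upper thresholds of 6, 8, 12 and 18 mEq/L and leaves the other direction to judgment. At stake is a patient who entered below 135 mEq/L being taken below the starting value by the rescue treatment.

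**Working it through.** **Inputs from the protocol.** D5W at 3 mL/kg per hour; start at hour 6; earliest stop at hour 14; expected fall 1 to 2 mEq/L per hour (6.2.6). Pilot net output 1360 mL over 24 hours (section 2, Table 1). A rise of 7 is the smallest whole-number rise that triggers the rule.

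**Stated figure reproduced.** 3 mL/kg × 70 kg = 210 mL per hour, as 6.2.6 says. Over 14 − 6 = 8 hours this is 24 mL/kg, or 1,680 mL at 70 kg. The 1 to 2 mEq/L per hour cannot be derived from the documents and is taken as given.

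**Reading 1: the stated rate is the net fall.** End value = rise − rate × hours.
- 1 per hour: 7 − 8 = 1 below baseline.
- 2 per hour: 7 − 16 = 9 below.
- Start delayed to hour 8 (assumed): 7 − 6 = 1 above, to 7 − 12 = 5 below.

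**Reading 2: simple dilution.** Fall = Na × V/(TBW + V), with V = 0.024 L/kg. Assumed: body water (TBW) 0.45-0.60 L/kg, all D5W retained, no further water loss. Hour-6 sodium is 132-141, that is, baselines of 125-134 plus 7.
- Na 132, TBW 0.60: 132 × 0.024/0.624 = 5.08, ending 1.9 above.
- Na 141, TBW 0.45: 141 × 0.024/0.474 = 7.14, ending 0.1 below.
- The hourly fall averages 0.6 to 0.9, below the stated 1 to 2. A fall of 16 by dilution would need TBW = 0.024 × (Na/16 − 1), or 17-19% of weight.

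**Reading 3: the stated rate is gross, partly offset by continuing water loss.** Pilot net output is 1360/24 = 56.7 mL per hour, which is 27% of 210. Treating this as an offset of the same size assumes that the lost fluid is electrolyte-free water and that stable pilot patients are a fair guide.
- 1 per hour: 7 − 8 × 0.73 = 1.2 above.
- 2 per hour: 7 − 16 × 0.73 = 4.7 below.
- Offset that brings the patient exactly to baseline: 1 − 7/8 = 12.5% at 1 per hour; 1 − 7/16 = 56% at 2 per hour.

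**Check of the proposed hold** (hold at 4 or less above baseline, restart at 6 or more, 2-hourly checks).
- Rise 7, net 2 per hour: hour 8 is 7 − 4 = 3 above, held there.
- Rise 7, net 1 per hour: hour 10 is 7 − 4 = 3 above, held there.
- Worst case, a rise just over 8 at net 2 per hour: for 8.1, hour 8 is 4.1 (not held) and hour 10 is 0.1 above (held). Over rises of 6.1 to 12, rates of 1 to 2 and the patient's own rise continuing at 0 to 1.17 per hour, the lowest value to hour 14 is about 0.1 above baseline. Under the current rule it is 6.1 − 16 = 9.9 below.
- Delay in acting on the result (assumed): 30 minutes gives 0.1 − 1 = 0.9 below; 1 hour gives 0.1 − 2 = 1.9 below.
- Rebound: if the patient's own rise of 7/6 = 1.17 per hour continues against D5W at 2 per hour, the net fall is 0.83 per hour. Hour 10 is 7 − 4 × 0.83 = 3.7 (held), hour 12 is 3.7 + 2.3 = 6.0 (restarted), and hour 14 is 6.0 − 1.7 = 4.3 above. Without a hold, hour 14 would be 7 − 8 × 0.83 = 0.3 above.

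**The case against.** The strongest counter-case is that D5W here is a brake on a continuing rise. Item 6 of 10.1 describes the aim as limiting further increases, and 6.2.5 attributes the risk to "overcorrection of serum sodium due to excess aquaresis and inadequate per oral intake". If aquaresis continues, the true net fall is smaller than 1 to 2 per hour. Dilution alone, with every millilitre retained, reaches no lower than 0.1 below baseline for a rise of 7. A reader might infer from the stated rate that the rule drives patients 9 mEq/L below baseline. The documents do not support that: the figure needs the upper rate for the full 8 hours with no offset. This part of the objection stands. It does not remove the gap, because 2 per hour with a modest offset still ends several mEq/L below, and the protocol does not say which reading is meant.

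The second argument is that safeguards exist: 2-hourly labs, at least 24 hours of observation, and a 20-hour recheck of which 6.2.6 says "these values will be reviewed prior to their discharge from the hospital setting". There is also symptom monitoring ("Patients found to be hyponatremic will also be monitored for development of symptoms during the study related to reduced serum sodium"), a Day 3 recheck, and the statement in 5.5.1 that investigator-judged safety overrides the protocol. A physician who sees sodium below baseline may stop D5W without breaching the plan. This stands as mitigation, but none of these supplies a limit.

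Third, a hold can let sodium rebound, which is the risk the rule exists to control. That also stands, so the hold needs a restart rule and clinical confirmation.

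Finally, read literally, a serum sodium above 18 mEq/L in 6.2.7 would include every patient. That inference fails: 10.1 item 9 shows that a rise above baseline is meant. The three wording differences are editorial and add no weight to the main point.

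**Conclusion.** The missing lower limit is certain from the text of 6.2.6 and 10.1. The undershoot is possible, not certain. For a rise of 7 treated from hour 6, the end value runs from 9 below baseline (upper stated rate, wholly net) to about 2 above (dilution, 60% body water), with about 4.7 below at 2 per hour gross and a 27% offset. The dilution range rests on assumed body water and full retention; the 27% rests on pilot data from stable patients.

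Severity is minor. Section 10.1 expects 3 to 4 hyponatremic patients, about 2 on tolvaptan at 1:1, and only those rising more than 6 by hour 6 qualify. The documents do not give that rate; the nearest figure is 2.2% of tolvaptan patients in the SALT trials with a rise above 12 in any 24 hours, which is a different event. A non-hyponatremic patient could also enter through 6.2.5. No endpoint, efficacy analysis or power figure is affected.

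**What to change.** Add to 6.2.6 (second bullet) and 10.1 item 7:

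> D5W will be held before hour 14 if any 2-hourly serum sodium is ≤ 4 mEq/L above baseline. Two-hourly checks continue to hour 14, and D5W restarts if the rise is ≥ 6 mEq/L. At hour 14, D5W is continued or restarted if the rise is ≥ 8 mEq/L, with 2-hourly checks until it is < 8 mEq/L.

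The hour-14 sentence is needed because the present text says when D5W stops, not when a held infusion resumes. The margin of 4 is a proposal: 2 hours × 2 mEq/L per hour, the largest stated fall between checks. It must be confirmed clinically, since laboratory delay uses it up and an early hold allows some rebound.

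In 6.2.6 (first bullet) and 10.1 item 6, state whether the 1 to 2 mEq/L per hour is net of continuing aquaresis.

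Consistency edits: use ≥ 12 in 10.1 item 8; add the reference to baseline after 18 mEq/L in 6.2.7 and after 12 mEq/L in the Appendix A footnote.

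The cost is protocol wording. With an hour-6 start, draws at hours 8, 10, 12 and 14 already fall within the minimum infusion, so nothing is added up to hour 14. If dosing is already complete, correct the text for reuse and check whether any patient given D5W ended below baseline.

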8. Patients with this degree of early increase in serum sodium will be observed for a minimum of 24 hours after their initial dose of study medication. They will also have repeat determination of serum sodium and other electrolytes plus BUN and Creatinine 20 hours after their initial dose of study medication and these values will be reviewed prior to their discharge from the hospital setting. If their serum sodium remains < 12 mEq/L above baseline at the 20 hour blood draw and they are clinical stable they will be discharged from the hospital setting at the 24 hour point. Any patient that is found to have a 20 hour serum sodium that is > 12 mEq/L from their baseline will receive additional D5W as above with repeat determinations of serum sodium until their value is < 12 mEq/L above their baseline. At that time if they are clinically stable then they will be discharged from the hospital setting.
9. Once discharged hyponatremia patients with overcorrection of sodium will be followed in the study but not treated further with study medication. They will return for a study visit Day 3 where they will have repeat determination of serum electrolytes, including serum sodium, as well as BUN and Creatinine. In the unlikely event that they are found to have serum sodium > 18 mEq/L above their baseline value at this visit, they will be considered for per oral hydration or administration of additional intravenous D5W at the discretion of the clinical investigator.

10. Any patient found to have overcorrection (a rise in serum sodium of > 6 mEq/L at the 6 hour time point) will still continue to be followed in the study and treated with augmented loop diuretic and other medical approaches as needed. They will be seen at Day 8 for evaluation as planned for the protocol and continue to have 30 day follow-up as well as additional clinic visits at any point during the study.

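### After a 6-hour sodium rise above 6 mEq/L, discharge at hour 24 rests on a 20-hour value; with D5W off, no later sodium is timed before the 48-hour visit

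*Combined protocol and SAP*

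**What the plan says.** Section 6.2.6 and items 6 to 8 of the risk-minimisation list in 10.1 describe one pathway. It starts when sodium is more than 6 mEq/L above baseline six hours after the first dose.

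- **D5W and sampling.** D5W is given at a rate "which is expected to reduce serum sodium from 1 to 2 mEq/L per hour". Sodium and the other chemistries are "determined at 2 hour intervals during D5W administration".
- **Stopping D5W.** Two conditions must both hold: at least 14 hours since the first dose, "and the serum sodium is < 8 mEq/L above their baseline value". Item 7 of 10.1 has the same limit.
- **Discharge.** The stay is at least 24 hours, with a draw at hour 20. The sodium test is "If their serum sodium remains < 12 mEq/L above baseline at the 20 hour blood draw". If it is met and the patient is clinically stable, "they will be discharged from the hospital setting at the 24 hour point".
- **Failing the test.** Section 6.2.6 gives more D5W for a "20 hour serum sodium that is ≥ 12 mEq/L from their baseline". Item 8 of 10.1 words it differently: a "20 hour serum sodium that is > 12 mEq/L from their baseline will receive additional D5W".

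The next scheduled sodium is at Visit 2, 48 hours after the first dose (5.6, 6.2.7, 6.3.1). The flow chart and 5.5.3 state that sodium is monitored for 24 hours in these patients but give no draw times. Appendix A has a column for 8 to 24 hours with conditional sampling and no hour-24 draw. Section 6.2.5 sends patients without baseline hyponatremia down the same pathway if they show the same rise.

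**The concern.** The value that decides discharge is four hours old when the patient leaves. If D5W is already off, nothing in the schedule measures sodium in those four hours or in the 24 hours that follow. The general sections commit to 24 hours of sodium monitoring, and 10.1 reports that overcorrection is most often defined as a rise above 12 mEq/L over 24 hours. The detailed schedule therefore stops short of the time point at which that rise would be read.

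The stake is patient safety. Section 10.1 places the possible threshold for osmotic demyelination at a rise of 8 to 12 mEq/L, adds that most cases followed much larger rises, and says that the condition may be permanent or fatal. Augmented loop diuretic continues after discharge (6.2.7).

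**Working it through.** **1. Draw times.** If D5W starts at hour 6 and keeps running, the two-hourly draws fall at hours 8, 10, ... 20, 22 and 24. If D5W stops between hours 14 and 20, the last timed draw is hour 20. The interval to the next scheduled value is 48 − 20 = 28 hours, of which 24 − 20 = 4 hours are before discharge.

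**2. Who is at risk.** D5W stops only at a rise below 8. A patient off D5W with a 20-hour rise of 8 to under 12 has therefore climbed since the infusion ended. If it ended at hour 14, a 20-hour rise of 11 implies an average climb above (11 − 8)/6 = 0.50 mEq/L per hour.

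**3. What takes that patient past 12 by hour 24.** Rate needed = (12 − 20-hour rise)/4:

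| 20-hour rise (mEq/L) | Rate above which hour 24 exceeds 12 (mEq/L per hour) |
|---|---|
| 8 | (12 − 8)/4 = 1.00 |
| 9 | (12 − 9)/4 = 0.75 |
| 10 | (12 − 10)/4 = 0.50 |
| 11 | (12 − 11)/4 = 0.25 |

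At a 20-hour rise of 11, the climb already implied (above 0.50) is more than twice the 0.25 needed. Whether a climb would continue is an assumption; the documents give no rebound rate.

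**4. The whole path from stopping D5W.** From a rise just under 8 at hour 14 to above 12 at hour 24 needs an average above (12 − 8)/10 = 0.40 mEq/L per hour. If D5W works as the protocol expects, at the slower 1 mEq/L per hour from hour 6 to hour 14, 6-hour rises of 7, 10 and 12 become 7 − 8 = −1, 10 − 8 = 2 and 12 − 8 = 4. Passing 12 by hour 24 would then need sustained climbs above 13/10 = 1.3, 10/10 = 1.0 and 8/10 = 0.8.

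**5. D5W still running at hour 20.** From hour 6 to hour 20 is 14 hours, an expected fall of 14 × 1 = 14 to 14 × 2 = 28 mEq/L. To be still at 8 or more at hour 20, the 6-hour rise would have to be at least 8 + 14 = 22 or 8 + 28 = 36. Such a patient also keeps the two-hourly draws.

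**6. How many patients.** Section 10.1 expects 3 to 4 hyponatremic patients. At 1:1 allocation that is 3/2 = 1.5 to 4/2 = 2 on tolvaptan. The share with a 6-hour rise above 6 is not given, so about 0 to 2 enter the pathway, slightly more through 6.2.5. In the hyponatremia trials cited in 10.1, 5/225 = 2.2% of tolvaptan patients rose more than 12 in some 24-hour period. Applied to 1.5 to 2 patients, that is 1.5 × 0.022 = 0.03 to 2 × 0.022 = 0.04 expected. This is only a guide, because those trials started at 15 mg and this one gives 30 mg.

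**7. Wording.** In 10.1 item 8, discharge needs a rise below 12 and further D5W needs one above 12, so a rise of exactly 12 has no branch; 6.2.6 covers it. The Appendix A footnote gives the limit of 12 mEq/L without saying that it is a rise above baseline.

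**The case against.** The strongest reply is that the pathway is already cautious. Study drug is not given again, the stay is at least 24 hours, discharge needs clinical stability, 5.5.1 puts safety above the protocol and allows extra laboratory tests where volume depletion is suspected, and sodium is repeated on Day 3. A site could also read the 24-hour monitoring statements as calling for a late draw. With D5W working as expected, the rebound needed is steep (step 4) and the expected number of patients is far below one. All of this stands, and it limits the size of the point. It does not close the gap: none of these provisions times a sodium at hour 24 once D5W is off, and clinical stability is not a sodium measurement.

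Three stronger readings are tempting, and the documents do not support them.

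- *The discharge rule breaks the protocol's own 24-hour limit.* Section 10.1 reports 12 mEq/L in 24 hours as the most common definition in general use. The protocol's working trigger is the rise above 6 at six hours, which 10.1 item 10 itself calls overcorrection.
- *The limits of 8 and 12 contradict each other.* They govern different decisions, stopping D5W and leaving hospital.
- *Patients may be sent home while they still need D5W.* The text does leave this open for a rise of 8 to under 12 with D5W running, since discharge is not made conditional on D5W being off. But step 5 shows that D5W would have to work far less well than expected, and ending the infusion is implicit in leaving hospital. This merits a clarifying phrase and no more.

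**Conclusion.** The point holds as a cheap safety improvement. Followed to the letter, the sodium rule can release a patient who has rebounded after D5W stopped and whose rise passes 12 mEq/L by hour 24 without anyone having measured it. The detailed schedule also falls short of the 24 hours of sodium monitoring promised in the flow chart and 5.5.3.

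The text of the rules is clear, so confidence in the gap is high. Its practical size is small and uncertain: the rebound rates are assumed, and the count of patients entering the pathway rests on the protocol's own forecast of hyponatremia. Nothing here bears on the endpoints, power or analysis.

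**What to change.** In 6.2.6 and in 10.1 items 7 and 8:

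- Keep the 20-hour draw and add one sodium at hour 24 after the first dose, reviewed before discharge.
- Discharge only if that value is less than 12 mEq/L above baseline and the patient is clinically stable. A value of 12 or more follows the existing additional-D5W step, whose end point is unchanged.
- Write ≥ 12 in 10.1 item 8 to match 6.2.6, and add that the limit is above baseline to the Appendix A footnote.
- As a minor clarification, state that the initial D5W course has been stopped under the existing < 8 rule before discharge.

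The cost is one blood draw, and possibly a short wait for the result, in about 0 to 2 patients already under observation (slightly more through 6.2.5). The clarification has its own cost: in the very rare patient still on D5W at hour 20, it could prolong both the infusion and the stay. The new draw shortens the unmeasured interval only from 28 to 24 hours; its value is that it falls at discharge and at the 24-hour mark.
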